**FIGURE 1: STUDY DIAGRAM**

## 1. PURPOSE

Adolescence is a health paradox: it is the healthiest time of life, yet a time of great risk and vulnerability with potential for devastating long term consequences, including poorer health, school failure and academic underperformance, engagement in risky impulsive behaviors, abuse of substances, increased risk of accidents, relationship difficulties with peers and parents, and the development of emotional and behavioral disorders. Hence, there is an urgent need to identify novel modifiable mechanisms contributing to risk and vulnerability among teens.

The modifiable mechanism targeted in this study is ‘eveningness’. Teens who exhibit an evening circadian tendency (‘night-owls’) follow a delayed sleep schedule, increasing activity later in the day and both going to sleep and getting up later, compared to morning types (‘larks’). The circadian tendency toward eveningness during adolescence arises from a confluence of psychosocial, behavioral and biological factors and is an important contributor to, and maybe even cause of, vicious cycles that escalate vulnerability and risk for poor health and major forms of psychopathology. Indeed, eveningness is associated with an extremely wide-range of adverse outcomes including poorer academic performance, poorer self-regulation, greater use of substances, greater tendency for impulsivity and more depression and anxiety. While the basic biological shift toward eveningness during puberty may be difficult to modify, the psychosocial and behavioral contributors are modifiable. Moreover, modifying the psychosocial and behavioral contributors will eliminate key factors that exacerbate the pubertal biological shift.

This conceptualization derives from evidence that biological changes in the circadian system at puberty lead to a shift in sleep timing preferences toward a delayed sleep phase. This effect is compounded by psychosocial changes including less parental control, increased access to stimulating social activities (movies, music, internet, texting, cell phones) and intake of alcohol and substances that contribute to sleep disruption. The social influences are synergistic with biological tendencies toward phase delay and can spiral quickly into a pattern of extremely delayed bedtimes. Yet, school or work usually requires a fixed early wake-up time. These forces converge to constrain the time available for sleep, resulting in high rates of insufficient sleep among youth. Compounding the negative cycle, most attempts to “catch-up” on sleep occur on weekends with an extremely phase-delayed schedule. This is a critical problem because the human circadian system adapts more easily to phase delays; endogenous rhythms are able to re-set quickly to later bed and wake times, but have more difficulty accommodating to phase advances (earlier sleep schedules). The problematic result is that large numbers of youth are struggling with the burdens of eveningness, sleep deprivation and the consequences of repeated circadian shifts. This is of particular concern for rapidly developing teens because adequate sleep is critical for optimal brain development.

This research will advance current knowledge on the role of eveningness as a mechanism contributing to poorer outcomes during adolescence. We aim to reduce eveningness among 10-18 year olds via an innovative intervention; the Transdiagnostic Sleep and Circadian Intervention (TranS-C) which integrates elements from four evidence-based treatments (Cognitive Behavior Therapy for Insomnia, Interpersonal and Social Rhythm Therapy, Chronotherapy, and Motivational Interviewing) derived from basic research on the circadian system. We will randomly allocate adolescents (10-18 year olds) with an evening circadian tendency, and who are ‘at risk’ in at least one of five health domains (emotional, cognitive, behavioral, social, physical), to either: (a) TranS-C or (b) Psychoeducation. Measures will be taken pre-treatment, at the end of treatment, and at 6 and 12 months post-treatment.

We aim to evaluate if an intervention to reduce eveningness among adolescents improves sleep and functioning in five health-relevant domains (emotional, cognitive, behavioral, social and physical) in the short and long term. The major hypothesis to be tested is that TranS-C, relative to Psychoeducation, will

improve sleep and circadian function, advance the timing of the endogenous circadian phase via the dim light melatonin onset protocol (DLMO), and decrease risk across the five health domains (emotional, cognitive, behavioral, social, and physical).

## 2. METHOD

### 2.1. Study Design

Based in a university clinic, youth will be randomly assigned, stratified by sex and age (10-14, 15-18), in a 1:1 parallel group design, to receive either TranS-C or PE. Sibling pairs will be randomized to the same condition.

Assessors will be blind to treatment allocation. Sequentially numbered, opaque, sealed envelopes will be generated using a computer-generated random number list. A project coordinator will conduct randomization after all eligibility assessments are completed. Assessments will be conducted at baseline and at the end of treatment. The Committee for the Protection of Human Subjects approved the study.

### 2.2. Participants

Participants will be recruited through clinicians or advertisements. Individuals will be eligible if they (a) are between 10 and 18 years old, living with a parent or guardian, and attending a class/job by 9am at least 3 days per week; (b) are fluent in English; (c) are able and willing to give informed assent; and (d) report eveningness as demonstrated by scoring within the lowest quartile of the Children's Morningness-Eveningness Preferences Scale (CMEP; 27 or lower) and have a 7-day sleep diary showing a sleep onset time of 10:40pm or later for 10-13 year olds, 11pm or later for 14-16 year olds, and 11:20pm or later for 17-18 year olds at least 3 nights per week. In addition, this sleep pattern will have to have been present for the past 3 months. Finally, participants will have to fall into an 'at risk' range on measures of at least one of the five health domains reviewed above.

Exclusion criteria will be (a) an active, progressive physical illness or neurological degenerative disease directly related to the onset and course of the sleep disturbance; (b) evidence of obstructive sleep apnea, restless legs syndrome, or periodic limb movement disorder; (c) significantly impairing pervasive developmental disorder; (d) bipolar disorder, schizophrenia, or another current Axis I disorder if there is a risk of harm if treatment is delayed. Participants will cease taking medications that alter sleep (e.g., hypnotics) 4 weeks prior to the assessment (2 weeks for melatonin) or will be excluded. Finally, history of substance dependence in the past six months or current suicide risk sufficient to preclude treatment on an outpatient basis will be exclusionary.

In other words, receipt of another sleep treatment will be the only type of treatment excluded. We want to be sure that any improvements in sleep could be attributed to TranS-C or PE, not the other sleep treatment. Other medications will be allowed. A medication-free group would be unrepresentative. We will also include youth with Axis I psychiatric comorbidity (except for bipolar disorder and schizophrenia), even if they are receiving treatment for that comorbidity.

### **2.3.1. Transdiagnostic Sleep and Circadian Intervention for Youth (TranS-C)**

TranS-C is grounded in sleep and circadian basic science and combines elements from four evidence-based interventions: Cognitive Behavior Therapy for Insomnia, Interpersonal and Social Rhythm Therapy, Chronotherapy and Motivational Interviewing (See Table 1). TranS-C is a modular approach which allows the treatment sessions to be focused on the specific sleep problem experienced by each patient. The goal is to reverse maintaining psychosocial, behavioral and cognitive processes via 4 cross-cutting modules, 4 core modules and 7 optional modules.

- The four *Cross Cutting Modules* are: case formulation; education; behavior change and motivation; goal setting. “Cross-cutting” modules are introduced in the first session and are typically featured every session thereafter.
- The four *Core Modules* are: establishing regular sleep-wake times including learning a wind-down and wake-up routine; improving daytime functioning; correcting unhelpful sleep-related beliefs; and maintenance of behavior change. “Core modules” apply to the vast majority of patients.
- The *Optional Modules* are: improving sleep efficiency; reducing time in bed; dealing with delayed or advanced phase; reducing sleep-related worry/vigilance; promoting compliance with CPAP/exposure therapy for claustrophobic reactions to CPAP; negotiating sleep in a complicated environment and reducing nightmares. “Optional modules” are used less commonly and only if indicated by the case formulation.

The modular format will allow the treatment sessions to be focused on the specific sleep problem experienced by each patient. The treatment manual recommends a specific order in which modules are typically completed but suggests that clinicians be sensitive to differences between patients as to which processes are maintaining their distress and to address those processes at an earlier stage of treatment. Specific assessments are recommended to guide the treatment provider as to when the optional modules should be used.

### **2.3.2. Psychoeducation (PE)**

Psychoeducation (PE) is an active comparison treatment associated with sleep improvement. PE constitutes a conservative control for treatment location, experience and skill level of the therapists, the number and quality of handouts, therapist attention, amount and frequency of contact with the therapist, duration of treatment, and beliefs and expectations about the efficacy of treatment held by the teens. Sessions will focus on the inter-relationship between sleep, stress, diet, health, exercise, accidents, and mood. These sessions will involve obtaining a detailed description from the teen about their experience with the topic and general education. Participants will also be given the choice of sampling meditation, yoga, and/or outdoors appreciation. There will be no explicit focus on sleep except briefly mentioning sleep as a common contributor to each topic. If a participant raises issues related to sleep or requests

advice on implementing change, the therapist will respectfully return to the content of the session. The emphasis will be on providing information but not on specifically facilitating behavior change.

### **3. MEASURES**

Except where specified, assessments will be administered before and after treatment. Assessments will be audio recorded. A random subset will be reviewed.

#### **3.1. Diagnosis**

The KSADS will be administered separately to youth and one parent/caregiver to assess for participant current and lifetime Axis I disorders at the pre-treatment assessment.

#### **3.2. Sleep Outcomes**

##### **3.2.1 Sleep Diary.**

An a priori decision was made to investigate weeknight average total sleep time (TST) and bedtime (BT) average as primary outcomes to best capture the sleep problems of interest. Secondary outcomes will be the discrepancy between weeknight and weekends for TST, BT, and waketime (WUP). Trained research assistants will phone the participants each morning to collect their sleep diary. In scheduling the call, the participants will specifically be told to not use the call as an alarm clock and to select a time as close as possible to rise time but after they are already out of bed. The training of the research assistants will specifically include not engaging in conversation other than collecting the sleep diary data. (See Table 2 for calculations of sleep diary variables).

Other secondary outcomes will be *Sleepiness Scale*, *Pittsburgh Sleep Quality Index (PSQI)* and *CBCL Sleep Composite (parent report)*.

#### **3.3. Circadian Outcomes**

##### **3.3.1 Children's Morningness-Eveningness Preferences Scale (CMEP)**

CMEP will be a primary outcome. Scores range from 10 (Extreme evening preference) to 43 (Extreme morning preference).

##### **3.3.2 Dim Light Melatonin Onset (DLMO)**

DLMO will be a secondary outcome. DLMO is the gold standard index of the endogenous circadian phase. DLMO is defined as the interpolated time at which melatonin exceeds 3.0 pg/ml. The selection of this threshold is based upon prior experience with melatonin as a marker of circadian phase and the visual inspection of each participant's DLMO record. This method of DLMO assessment will also provide a circadian phase estimate for the highest percentage of participants, including participants with low melatonin production.

Melatonin is a hormone produced by the pineal gland; its levels remain low during the daytime, begin to increase approximately 2 hours prior to habitual bedtime, and peak in the first part of the night. Synthesis and production of melatonin is predominantly regulated by the light-dark cycle. Circulating melatonin levels are a preferred circadian marker because they are comparatively robust and less prone to masking from other external influences compared to measures like to core body temperature, cortisol, and heart rate. However, bright light in the evening can suppress or "mask" nighttime melatonin production,

which necessitates its measurement in dim light conditions.

DLMO will be assessed with the serial saliva sampling method one night before and after treatment in an overnight stay in the Psychology Department at UC Berkeley based on established protocol. Several methods have been used to assess melatonin, including its concentration in plasma or saliva and its metabolite (aMTS6S) in plasma or urine. We will collect saliva as it has become the preferred sampling method as it is non-invasive and more acceptable to patients. Light levels will be determined using Fisher Scientific Extech Light Meter 407026 (Pittsburgh, PA). Following current convention, dim light (<50 lux, but preferably <20 lux) will be initiated 1 hour before the earliest melatonin onset.

Thirteen saliva samples will be collected for each participant before and after treatment, beginning 5.5 hours before average bedtime (computed from 7 nights of sleep diary) and ending 30 minutes after average bedtime. Saliva (~1 ml) samples will be collected in 30-minute intervals in dim light (< 50 lux) using untreated Sarsedt Salivettes (Starstedt, Germany). Saliva samples will be centrifuged at 3300 RPM for 5 minutes. If <1mL saliva is yielded after centrifuging, samples will be centrifuged for an additional 5 minutes at 3500 RPM. Samples will be frozen and stored at -80 °C and later assayed for melatonin by SolidPhase (Portland, Maine) using radioimmunoassay test kits (APLCO Diagnostics, Windham, NH). Assay sensitivities will be 0.3 pg/mL and the minimum detectable dose will be 0.05 pg/mL. Mean intra- and inter-assay coefficients of variation (CV) will be 7.9 and 9.4%, respectively. Saliva samples will be collected from all randomized participants.

### **3.4. Functioning in five health domains.**

For each of the five health domains (i.e., emotional, cognitive, behavioral, social, and physical health), three clusters of composite scores will be calculated using the cumulative risk index by taking the mean of standardized summary scores for specific measures within that domain.

#### **3.4.1. Youth Self-Report Composite Risk Score.**

The first cluster will be the *Youth Self-Report Composite Risk Score (primary)* which will be derived from psychometrically validated questionnaires representing each of the five health domains.

- *Domain 1. Emotional health* will be indexed by a composite of the 17-item Children's Depression Rating Scale-Revised (CDRS; range 17-113; higher scores = worse depression) and the 39-item Multidimensional Anxiety Scale for Children (MASC; range 0-117; higher scores = worse anxiety).
- *Domain 2. Cognitive Health* will be indexed by a composite of the 20-item Attentional Control Scale (ACS) (range 4-80; higher scores = better attentional control) and the six school-related items from the Youth Social Adjustment Scale – Self Report (YSAS).
- *Domain 3. Behavioral Health* will be indexed by a composite of the 8-item Sensation Seeking Scale for Children and the Alcohol and Substance Use Questionnaire to assess consumption of caffeine, alcohol, and recreational drugs in the past 30 days (1-7 rating scale; higher scores= more frequent use). For the purpose of the present study we will add questions on caffeine and energy drinks to the latter.
- *Domain 4. Social Health* will be indexed by the average of three subscales (ie, friends, family, romantic relationships) from the Youth Social Adjustment Scale – Self Report (higher scores = more impaired adjustment).

- *Domain 5. Physical Health* will be indexed by the composite of the Modifiable Activity Questionnaire for Adolescents (MAQ; Calculated as the number of hours per week being active/exercising; higher scores = greater numbers of active hours) and the Physical Health Questionnaire-15 (PHQ-15; range 0-30; higher scores = worse somatic complaints).

### **3.4.2. Youth Ecological Momentary Assessment (EMA) Composite Risk Score.**

The second cluster will be the *Youth Ecological Momentary Assessment (EMA) Composite Risk Score* which will be derived from phone calls twice per day on weekdays and four times per day on weekends. The questions asked during the calls will be adapted from Silk et al. The rationale for including EMA is to index 'real world' functioning in each of the five health domains.

- *Domain 1. Emotional Health* will be indexed with a short version of the Positive and Negative Affect Schedule for Children; 4 items measuring positive affect and 5 items measuring negative affect will be rated on a 5-point Likert scale. A Positivity Ratio will be calculated. Diener proposed that a high ratio of positive to negative emotion (the positivity ratio) predicts subjective well-being. Prior research has shown that sleep deprivation and eveningness are associated with a lower positivity ratio.
- *Domain 2. Cognitive Health*. Using questions adapted from previous research, participants will be asked 'At the moment the phone rang, what were you doing?'. Participants will then be asked to rate their concentration, distractedness and focus related to this task on a 5 point Likert scale. The response to these ratings will be averaged.
- *Domain 3. Behavioral Health*. Participants will be asked about eating, drinking or chewing gum or smoking at the moment the phone rang. We will tabulate the average weekly frequency and intake of junk food, caffeine, alcohol, nicotine and other substances.
- *Domain 4. Social Health*. We will assess who the participant is with at the time of the call. Positivity Ratio (see EMA for Emotional Health) will be calculated when the participant is alone, with a family member or with a friend.
- *Domain 5. Physical Health*. Physical activity will be assessed using questions from previous research. We will calculate a total of the binary variable (active = 1 and inactive = 2).

The Youth Ecological Momentary Assessment (EMA) Composite Risk Score will be derived by taking the average scores for the week for each domain.

### 3.4.3. Parent-Reported Composite Risk Score via the Child Behavior Checklist (CBCL).

The third cluster will be the *Parent-Reported Composite Risk Score* comprised of a composite score of parent responses to CBCL subscales representing the five health domains. Parents will rate this 113-item assessment of psychological and behavioral functioning of their child (rating scale 0-2; higher scores = more problematic behaviors). CBCL subscales will be used as the parent-reported composite risk score.

- *Domain 1. Emotional Health* will be assessed with the Anxious/Depressed and Withdrawn/Depressed subscale.
- *Domain 2. Cognitive Health* will be assessed with the Thought Problems and Attention Problems subscale.
- *Domain 3. Behavioral Health* will be assessed with the Rule-Breaking Behavior and Aggressive Behavior subscale.
- *Domain 4. Social Health* will be assessed with the Social Problems subscale.
- *Domain 5. Physical Health* will be assessed with the Somatic Complaints subscale.

### 3.5. Medications Tracking Log.

A Medications Tracking Log will be completed.

### 3.6. Credibility/expectancy questionnaire (CEQ)

The CEQ will be administered at the end of the second therapy session to index expectation of improvement and credibility of treatment.

## 4. TIMELINE FOR ASSESSMENTS AND TREATMENT

Study flow is illustrated in Figure 1. Adolescents and parents/guardians will be screened via telephone. Eligible adolescents will complete a sleep diary for 7 nights to ascertain the presence of Inclusion. If met, an in-person assessment will be conducted during which the KSADS and questionnaires will be completed. If the participant continued to meet criteria, the activities from this point forward will be conducted within the school semester because holiday schedules differ markedly during adolescence.

To determine DLMO collection times and wake-up times, an additional 7 nights of sleep diary will be collected immediately prior to the overnight stay in the lab. The overnight assessment of DLMO will be conducted in the Psychology Department at the University of California, Berkeley and will be held on a Friday or Saturday night. The rationale for this choice is to ensure the protocol doesn't interfere with school. Groups of 1 to 5 participants will be tested each evening. Each participant will have their own bedroom. We will ensure the participant is exposed to <50 lux at all times, but prefer <20 lux. The lighting in each bedroom will be replaced with dim light bulbs. When the participant leaves the bedroom (e.g., to go to the bathroom) they will wear welding glasses. A light metre will be used to check the illumination of computer and cell phone screens. The light meter will be held next to participants eyes to measure the amount of light the participant is exposed to. Across the evening the participants will be allowed to engage in a narrow range of tasks that represent a standardized regimen of calm/quiet activities (e.g., reading, playing a board game, watching a movie, completing homework). We will assist the participants to set their computers/phones to the lowest brightness. In order to complete the DLMO protocol, the participant will stay up 45 minutes later relative to their usual school day bedtime. To minimize the impact of this, we will allow the participants to sleep in by 30 minutes relative to their usual school day waketime. The participant will arrive approximately 6.5 hours before their bedtime. If participants ingest anything except water before the saliva sample, they will rinse their mouths and

brushed their teeth with water. Ingestion of caffeine, fruits, chocolate, non-steroidal anti-inflammatory drugs, and alcohol will be prohibited.

After the overnight, the participant will be randomized and complete a further 7 night sleep diary and answer phone calls to collect Ecological Momentary Assessment (EMA) data. This additional sleep diary will be collected so that sleep diary data will be concurrent with EMA. These measures will be the basis of the primary and secondary outcomes. Treatment will commence one week later.

After treatment, the procedures for the overnight assessment to collect DLMO will be repeated, along with an in-person interview and 7-days of EMA and sleep diary. The participants will be reimbursed \$30 for participating in the pre- and post-treatment assessments and \$40 for the 6-FU and 12-FU. Parents will be reimbursed \$30 for participating in the pre- and post-treatment assessments, \$20 for the 6-FU, and \$20 for the 12-FU.

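### The DLMO night can be Friday at one visit and Saturday at the other, which may add avoidable noise to the secondary DLMO contrast

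*Combined protocol and SAP*

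**What the plan says.** Section 4 (Timeline for Assessments and Treatment) states that the DLMO overnight "will be held on a Friday or Saturday night". The reason given is practical: "The rationale for this choice is to ensure the protocol doesn't interfere with school". For the second visit the section says only that "the procedures for the overnight assessment to collect DLMO will be repeated". What is repeated therefore includes the choice between two nights.

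Section 3.3.2 sets the number of nights: "DLMO will be assessed with the serial saliva sampling method one night before and after treatment". No averaging within a visit can smooth out a night effect. The same section gives the outcome its rank: "DLMO will be a secondary outcome".

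Section 1 (Purpose) describes the population's catch-up sleep, most of which is said to "occur on weekends with an extremely phase-delayed schedule". It adds that "endogenous rhythms are able to re-set quickly to later bed and wake times".

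The model in Section 5 (Data Analysis) has fixed effects for age, sex, time, treatment and the time-by-treatment interaction. Night of the week is not among them. The section also commits to reporting the pre-to-post change within each arm whatever the interaction shows.

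**The concern.** A Friday session usually comes after a school night and a school morning. A Saturday session comes after a free Friday night and a free Saturday morning. Section 4 ties bed and wake times on the laboratory night to the school-day schedule, but no section controls the night before. Given what Section 1 says about weekends, the two nights may not be interchangeable as readings of circadian phase.

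If they are not, a participant whose night switches between visits carries the Friday-Saturday difference in the change score. Friday then Saturday looks like a delay; Saturday then Friday looks like an advance. Advancing DLMO is part of the major hypothesis in Section 1, and the only other circadian outcome (CMEP) is a preference scale. Precision in the DLMO contrast is therefore worth protecting, especially as Section 4 already standardizes light, activity, food intake and semester timing.

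**Working it through.** **Inputs from the documents.** Either night allowed, no matching across visits (Section 4); one night per visit (Section 3.3.2); treatment effect is the difference in mean pre-to-post change (Section 5); randomization follows the baseline overnight (Section 4); 1:1 allocation (Section 2.1); standardized effect 0.48, significance level 0.05, power at least 80%, 69 per condition (Section 5).

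**Inputs that are assumptions.** Saturday-minus-Friday offset d: 15, 30 or 45 minutes. SD of individual DLMO change with no night effect: 60 minutes. Probability p that a visit falls on Saturday: 0.5, independently at the two visits. The documents give none of these.

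**The plan's own figure.** n per arm = 2(1.960 + 0.842)²/0.48² = 68.1, rounded up to 69, two-sided, with power 80.5% at 69. (An exact t-test calculation gives 69.1, with 79.9% power at 69.) The figure reproduces. It is not specific to DLMO and is borrowed below only as a yardstick.

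**Added variance.** With complete pairs, the interaction equals the between-arm difference in mean change, so the variance of change is what matters. The night contributes d × (Saturday post − Saturday pre) to each change score. At p = 0.5 this is −d, 0 or +d with probabilities 0.25, 0.5 and 0.25: mean zero, variance 0.5d². In general the variance is 2p(1 − p)d².

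The base variance is 60² = 3,600 min². The true effect is 0.48 × 60 = 28.8 minutes.

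| d (min) | Added variance | Share of 3,600 | New SD | Standardized effect | Power at 69 per arm | n per arm for 80% |
|---|---|---|---|---|---|---|
| 15 | 112.5 | 3.1% | 60.9 | 0.473 | 79% | 71 |
| 30 | 450 | 12.5% | 63.6 | 0.453 | 76% | 77 |
| 45 | 1,012.5 | 28.1% | 67.9 | 0.424 | 70% | 88 |

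The last column multiplies 68.1 by 1.031, 1.125 and 1.281 and rounds up.

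**Sensitivity to the SD.** With the SD between 45 and 75 minutes, power is 78-80% for d = 15 and 72-77% for d = 30. A 60-minute offset would give 54-69%.

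**Sensitivity to the mix of nights.** p = 0.5 is the worst case for independent visits. At p = 0.8 the factor is 2 × 0.8 × 0.2 = 0.32, so d = 30 adds 0.32 × 900 = 288 min², or 8% instead of 12.5%. If families tend to book the same night twice, with correlation r between visits, the factor is multiplied by (1 − r).

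**Bias in the interaction.** For a constant offset, bias = d × the between-arm difference in net Friday-to-Saturday switching. It is zero when switching is balanced. A 10-point imbalance gives 0.1 × d = 1.5, 3 or 4.5 minutes.

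**Within-arm changes.** If the share of Saturday sessions moves by 20 points between visits in both arms, each arm's change shifts by 0.2 × d = 3, 6 or 9 minutes, while the interaction is untouched.

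**After matching.** With the same night at both visits, the night term is zero for every participant. A constant offset cancels and the added variance is 0.

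**The case against.** The strongest reply is that the size of the problem is entirely assumed. Section 1 describes quick re-setting in order to contrast delays with advances, and gives neither minutes nor a number of nights. A reader might infer that the protocol itself says one free night delays DLMO. It does not; that step is an inference. This objection stands, and at d = 15 minutes the loss is trivial.

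A reader might also infer that the DLMO treatment contrast is biased, or biased towards delay. The documents do not support that. The artefact runs in both directions. The baseline night is fixed before randomization, both arms have six weekly sessions and the same repeated procedures, and nothing suggests that post-treatment booking would differ by arm. One route remains open: regularizing sleep-wake timing is a core part of TranS-C (Section 2.3.1), so treatment could shrink the Friday-Saturday offset itself. The estimated effect would then depend on the mix of nights. That is possible but not shown.

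Three smaller points also stand. Eligibility requires an early class or job on as few as three days a week (Section 2.2), so a Friday session need not follow a school night. The 60-minute SD would double-count the night effect if it came from data that already mixed nights. DLMO is secondary and the sample size does not rest on it; the primary outcomes are unaffected.

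None of this answers the gap itself. Repeating the procedures does not imply repeating the night, and the model cannot separate the two.

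**Conclusion.** The point holds as a cheap improvement to a secondary outcome. A participant's DLMO nights can differ between visits, and the plan neither prevents this nor adjusts for it. The expected consequence is non-differential noise of unknown size. On the assumptions above (SD of change 60 minutes, p = 0.5, independent visits), variance rises by about 3% to 28% for offsets of 15 to 45 minutes, and by less for other mixes or correlated bookings. The reported within-arm changes are also open to any overall drift between Friday and Saturday, from which randomization does not protect them. The interaction is biased only if post-treatment nights differ by arm or if treatment alters the offset, and the documents establish neither.

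**What to change.** In Section 4, add that each participant's post-treatment overnight is booked on the same night of the week as the pre-treatment one wherever possible, without losing or unduly delaying a sample to achieve it. Record the night, and report it by arm and visit.

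In Section 5, add two sensitivity analyses for DLMO: one with a time-varying Friday/Saturday indicator, and one restricted to participants with the same night at both visits. Both have limits to state. A single indicator assumes one offset for both arms and both visits, so it would not capture an offset that treatment shrinks. The same-night subset is defined after randomization and is supportive only. Matching likewise cancels only a constant offset, which is why the night should be reported by arm and visit. If overnights have already been held, session dates, where kept, would still allow both analyses.

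The cost is one sentence in the protocol, one recorded item and two short analyses. The downside is less booking flexibility within the school semester and within sessions of one to five participants. No extra visits or samples are needed.
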